### **Opportunistic infection**

All TEAEs identified using UCB-defined search criteria as described in Section 12.13.

90cr

### Malignant or unspecified tumor

The search criteria is based on the Standardized MedDRA Query (SMQ) = "Malignant or unspecified tumours (SMQ)".

### Malignant tumor

The search criteria is based on the SMQ="Malignant tumours (SMQ)".

### Major cardiovascular events

lations thereof The major cardiovascular events are identified using the following UCB-defined search criteria:

- All serious TEAEs which code to a PT included in the Scope=Broad and/or Scope=Narrow groups of the following SMQs:
  - Haemorrhagic central nervous system vascular conditions (SMQ)
  - Ischaemic central nervous system vascular conditions (SMQ)
- All serious TEAEs which code to a PT included in the HLT "Ischaemic coronary artery disorders" except events coding to PT "Chest Pain" or "Chest discomfort"
- All serious TEAEs which code to a PT included in any of the following HLTs: "Heart Failures NEC", "Left Ventricular Failures", or "Right Ventricular Failures" and which also code to the SOC of "Cardiac Disorders" as Primary SOC.

### Haematopoietic cytopenias

The search criteria is based on the SMQ = "Haematopoietic cytopenias". The SMQ search should include all serious TEAEs which code to a PT included in the Scope=Broad and/or Scope=Narrow groups within the SMQ.

### **Neuropsychiatric events**

The search criteria is based on the SMQ = "Depression and suicide/self-injury (SMQ)". The SMQ search will include all TEAEs which code to a PT included in the Scope=Broad and/or Scope=Narrow groups within the SMQ.

## Inflammatory bowel disease

All TEAEs which code into the HLT of "Colitis (excl infective)" are identified as inflammatory bowel disease.

## Hypersensitivity reactions and anaphylactic reactions

Hypersensitivity reactions and anaphylactic reactions will be identified as follow:

- a) Hypersensitivity reactions: All TEAEs that either emerged on the same day as when a study medication injection reaction was received, or that emerged one day after a study medication injection was received, which code to a PT which contains the term "hypersensitivity" will be considered to be a hypersensitivity reaction and included in the summary table as such.
- b) Anaphylactic reactions: An algorithmic approach will be used to identify TEAEs that are considered to be anaphylactic reactions. PTs are separated into the 4 distinct categories (A, B, C, D) prior to the algorithmic approach being applied.

All TEAEs that either emerged on the same day as when a study medication injection reaction was received, or that emerged one day after a study medication injection was received, and variations thereof which fulfill any of the 3 criteria described in Section 12.14 will be included in the summary table.

## Hepatic events

The search criteria is based on all TEAEs in the SMQ "Drug related hepatic disorders comprehensive search (SMQ)". Note that the following two sub-SMQs are to be excluded: "Liver neoplasms, benign (incl cysts and polyps)" and "Liver neoplasms, malignant and unspecified (SMQ)".

The SMQ search should include all TEAEs (regardless of whether they have been judged as related to study medication or not) which code to a PT included in the Scope=Narrow group within each SMQ.

#### 4.3.2 Interim analysis Week 48

After all enrolled subjects have completed the Week 48 or Early termination visit, a second interim analysis will be performed to analyze the key efficacy and safety data for the whole treatment period.

No separate SAP for that interim analysis will be provided. This interim analysis is a subset of the final analysis and will focus on the primary and secondary efficacy analysis. The TFL shells for the final analysis will be used.

The snapshot for the AS0008 interim analysis Week 48 will occur before all subjects have completed the AS0008 study. Specifically, subjects who do not enter the extension study will need to complete the SFU Visit, which occurs 20 weeks after the last dose of study treatment. The Week 48 interim database lock will be performed based on the last subject completing the Week 48 visit. It is anticipated that there will be some subjects still awaiting the SFU at that time. The number of subjects in the SFU period is expected to be low, and the minimal data to be collected from their SFU visits is not considered mandatory to evaluation of the key efficacy and safety objectives of the study.

#### Changes from interim analysis to SAP-defined analyses 4.3.2.1

The baseline definition for CRP and hs-CRP measurements were updated with the fifth SAP Amendment after the interim analysis. The interim analysis used the previous definition: The last valid measurement before first dose of study drug (Visit 2) will be used as the Baseline vale.

#### Use of an efficacy subset of subjects 4.6

The primary dose-response analysis and pairwise comparisons will be repeated for (1) all subjects in the PPS, and (2) for all subjects in the RS as a supportive analysis. The purpose is (1) to evaluate the effect of important protocol deviations on the analysis, and (2) to evaluate the consistency of the FAS with the intent-to-treat (ITT) principle.

#### 4.7 Active-control studies intended to show equivalence

Not applicable.

#### Examination of subgroups 4.8

The following variables for subgroup analyses will be used:

- Age (<45 years, ≥45 years)
- Gender (male, female)
- Geographic region (North America, Eastern and Western Europe)
- Treatment-emergent AbAb status (positive, negative) •
- Prior TNF inhibitor exposure (yes, no) •
- Current NSAIDs at Baseline (yes, no)
- BASDAI (<4 [mild disease];  $\geq$ 4 to  $\leq$ 7 [moderate disease]; >7 to  $\leq$ 10 [severe disease])

Subjects will be counted to have a positive treatment-emergent AbAb status in case the first AbAb positivity occurred up to Visit 7 (Week 12). The definition of first AbAb occurrence is This docu described in Section 9.2.

### STUDY POPULATION CHARACTERISTICS 5

### 5.1 Subject disposition

Loon for screen failures Loon of subjects screened will include the Loo, LOS, and DBRS) overall and by site. The number and percentage of subjects who discontinued study medication, who discontinued for the study, and who discontinued due to AEs will be summarized for subjects in the RS. Study eligibility criteria will be listed and a separate listing of the eligibility criteria will be presented. Onto a subject of the Subject of the study of the summarized for subjects in the RS.

Subject disposition will be listed for all subjects screened and will include, inter alia, the following information: subject status, date of informed consent, randomization, first and last study medication, and primary reason for premature study termination. Listings of subject analysis sets, study and study medication discontinuation, and visit dates will be presented by subject including the relative study day (calculated as described in Section 3.2.1) for each visit.

### 5.2 **Protocol deviations**

Important protocol deviations will be identified and classified by the deviation types. Following different important protocol deviation types will be classified: inclusion criteria deviation, exclusion criteria deviation, withdrawal criteria deviation, prohibited concomitant medication use, incorrect treatment or dose, treatment non-compliance, and procedural non-compliance.

Summary tables of the number and percentage of subjects with an important protocol deviation will be provided including a summary of subjects excluded from the PPS, PK-PPS, and PD-PPS due to important protocol deviations. Summary tables will be presented for FAS analysis sets.

A listing of all important protocol deviations identified at the data evaluation meeting will be presented by subject for all subjects in the RS, and will include deviation type and description.

## 6

This docu

## DEMOGRAPHICS AND OTHER BASELINE **CHARACTERISTICS**

### 6.1 Demographics

Tables with descriptive statistics (number of subjects, mean, SD, minimum, median, and maximum) and listings will be given for the demographic variables age (at time of informed consent), gender, racial group, ethnicity, weight at Screening, height at Screening, and body mass index (BMI). Age will be summarized as a continuous variable and as categorical variables based on the following categories:  $\leq 18$ , 19- $\leq 65$ ,  $\geq 65$  years (clinicaltrials.gov requirement) and 18- $<65, 65-<85, \geq 85$  years (EudraCT requirement).

BMI in kg/m2 is calculated based on the height (in m) and the weight (in kg) using the formula: For adults:

$$BMI = \frac{Weight}{Height^2} \tag{5}$$

Even if they are available in the database, these variables are calculated during analysis (if applicable). These calculated values are used in the statistical analysis since they are considered more accurate.

I ne summary tables will be performed on the SS and repeated using the FAS, and the DBS. If the SS and FAS analysis sets are identical the summaries will not be repeated. The Listing will be provided for all subjects screened, except the Lifestyle listing will use the RS. 6.2 Other Baseline characteristice AS history will be attended to a state of the summaries of the state of

AS history will be summarized for subjects in the FAS and SS including the time since first diagnosis of AS, time since first symptoms of AS, and age at first diagnosis date. The history will be listed for all subjects in the RS. andany

Time since first diagnosis of AS will be calculated as:

$$Time since first diagnosis (years) = \frac{Date of Informed Consent - Date of diagnosis + 1}{365.25}$$
(6)

If the date of diagnosis is partial, it should be imputed to the most recent feasible date (ie, last day of the month if only day is missing, or the last day of the year if day and month are missing).

Time since first symptoms will be calculated as:

$$Time since first symptoms (years) = \frac{Date of Informed Consent - Date of first symptoms + 1}{365.25}$$
(7)

Age at first diagnosis will be calculated as:

$$Age \ at \ first \ diagnosis = \frac{Date \ of \ first \ diagnosis - Date \ of \ birth}{365.25} \tag{8}$$

These formulas may result in incorrect ages after rounding if the birth day falls on the date of first diagnosis. In that case the age is calculated as the number of years between the year of birth and the year of the randomization visit. The age for individual subjects is presented with 1 decimal The rounding is done downwards. For subjects enrolled at German sites, only the year of birth may be entered into the eCRF for this study. For these subjects age will be calculated after imputing their date of birth to be 01 Jan XXXX.

Baseline characteristics (including scores relevant for inclusion and exclusion criteria) will be summarized by treatment group and overall for FAS, SS, and DBS. Following variables will be summarized:

- BASDAI total score
- BASDAI spinal pain (question 2)

- **PGADA** •
- Total spinal pain (question 1 of the total and nocturnal spinal pain questionnaire)

The corresponding listings will be presented for the RS.

## 6.3

NSAID therapy, prior anti-TNF therapy (frequency counts) NSAID therapy, synthetic DMARDs, methotrexate, sulfasalazine, and hydroxychloroquine e corresponding listings will be presented for the RS. Medical history and concomiteration dical history and concomiteration Medical history and ongoing medical conditions will be summarized by MedDRA system organ class (SOC) and PT by treatment and overall including the number and percentage of subjects with each condition. The denominator for the percentages will be the number of subjects in the SS and FAS for each treatment or overall.

Medical history and ongoing medical conditions will be listed by treatment and subject including the reported term, PT, and SOC for the RS. The start date (month and year only) and end date (or ongoing if applicable) will also be included in the listing. A glossary of all medical history conditions will also be presented including the reported term, PT and SOC.

#### 6.4 Prior and concomitant medications

Prior medications include any medications that started and ended prior to the start date of study medication. Concomitant medications are medications taken at least one day in common with the study medication dosing period. For bimekizumab, the dosing period is typically from the date of first dose up to (but not including) one dosing interval post last dose. Thus, a concomitant medication is any medication whose start date is on or after the date of first study medication and prior to the date of last study medication administration + 28 days (1 dosing interval), or whose stop date is either missing, or on or after the date of first study medication administration.

In the case of missing data, the classification of medications as prior or concomitant will be performed as described in Section 4.2.3.

The number and percentage of subjects taking prior medications will be summarized by treatment group, overall and by anatomical therapeutic chemical (ATC) class, presenting Anatomical Main Group (ATC Level 1), Pharmacological Subgroup (ATC level 3), and PT.

The number and percentage of subjects taking concomitant medications will be summarized similarly in two tables separating between AS concomitant medications and concomitant medications. AS concomitant medications includes the following list: NSAIDS, corticosteroid, methotrexate, sulfasalazine, hydroxychloroquine. Tables for prior and concomitant medications will be presented for SS and FAS.

Prior and concomitant medications will be listed by treatment and subject for RS.

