## Double-Blind Period

At Baseline subjects will be randomized in a 1:1:1:1:1 ratio (stratified by region and prior TNF inhibitor exposure) to receive the following blinded study treatment regimens during the Double-Blind Period:

Placebo

Bimekizumab 16mg administered sc Q4W

- Bimekizumab 64mg administered sc Q4W
- Bimekizumab 160mg administered sc Q4W
- Bimekizumab 320mg administered sc Q4W •

The enrollment of TNF inhibitor-experienced subjects will be limited to approximately 30% of the total study population.

Subjects withdrawing early from the study will undergo the Early Termination Visit assessments and will enter the SFU Period. The investigational medicinal product (IMP) will be administered sc in the clinic at Baseline,

The Dose-Blind Period lasts from Week 12 to Week 48. Subjects randomized to bimekizumab 160mg Q4W or bimekizumab 320mg Q4W will remain on their randomized dose and subjects randomized to placebo, bimekizumab 16mg Q4W, and bimekizumab 64mg Q4W, will be rerandomized in a 1:1 fashion to bimekizumab 160mg Q4W or bimekizumab 320mg Q4W. The total duration of treatment is 48 weeks.

During the 36-week Dose-Blind Period, subjects will be evaluated for eligibility to rescue treatment at defined time points. Subjects who do not show an improvement in both PGADA and spinal pain compared to Baseline will be eligible to receive rescue therapy as defined in Section 6.5.

Section 6.5. Safety Follow-Up Visit/Extension study At the completion of the Dose-Blind Period, subjects will be given the opportunity to enter an extension study at Week 48. All subjects who complete the study and do not enter the extension study or who discontinue early, including those withdrawn from study treatment, will have a SFU Visit at 20 weeks after their last dose of IMP.

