#### 8.1.5 Sensitivity analyses of the primary efficacy variable

Two sensitivity analyses will be performed for the primary dose response analysis and for the supportive analysis number 3:

1. This analysis evaluates the effectiveness of the treatment (de facto hypothesis) and will be This documen based on the ordered categorical analysis to evaluate dose-response as specified in the primary analysis. In an attempt to prevent missing data during the study, efforts will be made to collect data from subjects that withdraw early from the study. An analysis will be performed in which all available data at Week 12 will be considered. In this case, subjects will be analyzed according to their randomized treatment, even if they discontinued prior to Week 12 and were no longer on the randomized study treatment when the assessment was performed at Week 12. If Week 12 data for the ASAS response are not collected, the subject will be assumed to be a non-responder. It should be noted that this measures something

different from the primary analysis and could be confounded by placebo subjects who withdraw and are subsequently on another active medication at the time of the Week 12 assessment.

2. An additional sensitivity analysis will be based on observed data only for subjects who are still on the initially randomized treatment at Week 12. Subjects with missing data or who have prematurely discontinued study treatment will be excluded from the analysis. The same procedure described for the primary efficacy analysis of dose response will be used.

The following sensitivity analyses will be performed for the secondary analysis for the primary efficacy variable (pairwise comparison analysis of the primary efficacy variable) in order to assess the missing data assumptions:

- Missing data will be imputed using MI. In MI, the missing value is replaced by a set of
  plausible values, where each value is a Bayesian draw from the conditional distribution of the
  missing data given the observed data. Intermittent missing data will be imputed using the
  MCMC method, followed by monotone regression for monotone missing data to evaluate the
  effect of the method for handling missing data on the analysis. The ASAS components will
  be imputed individually and then the ASAS response will be calculated using the complete
  datasets. The multiply imputed data sets will be analyzed using a logistic regression model

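### The concomitant-medication rule in SAP Section 6.4 joins its conditions with *or*, so drugs started after the dosing period count as concomitant

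*SAP*

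**What the plan says.** SAP Section 6.4 makes three statements in sequence.

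- Definition: "Concomitant medications are medications taken at least one day in common with the study medication dosing period".
- Dosing period: "the dosing period is typically from the date of first dose up to (but not including) one dosing interval post last dose".
- Operational rule, presented as following from the first two and made of two limbs. The first limb requires a start no earlier than the first dose; its upper limit, and the connector to the second limb, read "prior to the date of last study medication administration + 28 days (1 dosing interval), or whose". The second limb asks only that the drug has no recorded end, or an end no earlier than the first dose.

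The same section reserves the prior category for drugs that both started and ended before study medication. It tabulates concomitant drugs by treatment group for the SS and FAS, with a separate table for AS concomitant medications (NSAIDs, corticosteroid, methotrexate, sulfasalazine, hydroxychloroquine). Section 4.2.3 supplies dates where they are partial and does not otherwise limit the rule.

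Two other sections bear on the consequence. Under Section 2.3, subjects who discontinue, or who complete without entering the extension study, "will have a SFU Visit at 20 weeks after their last dose of IMP". Section 8.1.5 recognises that placebo subjects may "withdraw and are subsequently on another active medication at the time of the Week 12" assessment.

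**The concern.** The rule does not implement the definition it is drawn from. Its stop-date limb is sufficient on its own and sets no upper limit on the start date. A drug first taken well after the last dose, when the dosing period is over, therefore satisfies it.

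At stake is how the by-arm medication tables read. An NSAID or corticosteroid begun in the Safety Follow-up by a subject who had stopped study drug would appear in the AS concomitant table as if it had been co-treatment. Any other later therapy would appear the same way in the general table. If early discontinuation differs between arms, the tables would show a difference in co-medication that reflects treatment after study drug. Two programmers, one coding the definition and the other the rule, would also produce different tables.

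**Working it through.** The SAP gives no figure to reproduce, so the check is one of logic.

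**Notation** (all from Section 6.4)

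- F = date of first dose; E = date of last dose + 28 days.
- Condition A: F ≤ start < E.
- Condition B: stop missing, or stop ≥ F.
- Rule as written: A or B.
- Definition (at least one day inside F to E, E excluded): start < E and B.

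**Argument.** Take any drug with start ≥ E. Its stop date is missing, or is no earlier than its start, which is later than F. B is therefore always true and the written rule returns concomitant. The definition returns not concomitant, because start < E fails. Further, whenever A is true the start is at or after F, so the stop is missing or at or after F, and B is true as well. A never adds a case that B has not already caught. The written rule reduces to B alone, and the 28-day limit does nothing.

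**Enumeration.** F = day 1 and last dose at Week 8 = day 57, so E = 57 + 28 = day 85. Every start from day -100 to day 239 was paired with every stop from the start day to day 259, and with a missing stop.

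| Quantity | Pairs |
|---|---|
| All start/stop pairs | 65,110 |
| Pairs with start ≥ E | 15,345 |
| Of these, concomitant under the written rule | 15,345 |
| All disagreements, written rule against definition | 15,345 |
| Pairs meeting A but not B | 0 |
| Disagreements if A and B were joined by *and* | 26,260 |
| Disagreements for start < E and B | 0 (identical to the definition) |

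The pair counts depend on the grid and do not estimate how many records are affected. They show that every late start is misclassified and that nothing else is.

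The 26,260 disagreements under a plain *and* are drugs started before first dose and continued on treatment, which that version drops. The Section 13.5 change log shows that Amendment 5 replaced *and* with *or*. That brought the continuing drugs back in but removed the upper limit.

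**Example.** Last dose on day 57 and a new drug started on day 125 (E + 40): concomitant under the written rule, no overlap with days 1 to 84 under the definition.

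**Share of the follow-up interval.** Last dose to follow-up visit: 20 × 7 = 140 days. Outside the dosing period: 140 - 28 = 112 days. 112/140 = 80%.

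**The case against.** The logic is not disputed, but there are fair arguments on scope and consequence.

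- **Not all therapy after stopping is affected.** A drug begun after the last dose but within 28 days of it is concomitant by the SAP's own definition. This stands: only starts on or after last dose + 28 days are misclassified.
- **The AS table is restricted to five drug types.** A later biologic would reach only the general table. This stands, although the five listed types can themselves be started in follow-up.
- **The 80% is calendar time.** It counts neither records nor subjects, and it assumes that medication is recorded up to the follow-up visit, which the SAP does not state. Section 4.3.2 expects few subjects to be in follow-up at the Week 48 snapshot and describes their follow-up data as minimal. A completer's last planned dose is at Week 44, so E falls at about Week 48 and someone entering the extension has almost no exposed window. All of this limits the practical size.
- **Nothing inferential depends on it.** The classification feeds descriptive tables and listings. The ASAS40 analyses and the missing-data rules do not use it, and the listings show dates as recorded. This stands.
- **The intended meaning is clear from the preceding sentences.** A careful programmer might follow the definition. However, the rule is the more specific statement and was deliberately reworded, so it is the one likely to be coded.

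**Conclusion.** The concern holds: the rule is wrong as written. It contradicts the definition earlier in the same paragraph, and no other current section corrects it. Every medication started on or after last dose + 28 days is classed as concomitant.

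The matter is minor. It affects the descriptive concomitant and AS concomitant medication tables, chiefly for early discontinuers and for completers who do not enter the extension study, and leaves the efficacy inference untouched. The window for misclassification is 112 of the 140 days between last dose and the follow-up visit, assuming that the visit takes place at 20 weeks and that new medications are recorded until then. The number of records involved cannot be derived from the SAP.

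**What to change.** Replace the operational sentence in Section 6.4 with a rule under which a medication is concomitant if both of the following hold:

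1. it started before the date of last dose + 28 days; and
2. its stop date is missing, or is on or after the date of first dose.

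Drop the requirement that the start be on or after first dose. Simply changing *or* to *and* in the present sentence would lose drugs started before first dose and continued on treatment.

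Medications started on or after last dose + 28 days would then be neither prior nor concomitant. It is worth stating that they appear in the listing only, or under a separate post-treatment label.

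The cost is one sentence in the SAP and one line of program. No new data are needed.
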